Forty women ages 18–45 years will complete a protocol involving open-label treatment with standard-dose depot leuprolide to induce hypo-E2 in all women and generate HF in approximately 2/3, thereby mimicking menopause (see **Schema**). As part of the protocol, subjects will be admitted to the BWH Clinical And Translational Science Center/Center for Clinical Investigation (CCI) inpatient unit for a total of 10 nights over a 2-month period (see **Schema**). Assessments will be divided into 2 sleep blocks. Each SB includes 2 nights during which sleep is undisturbed and 3 nights during which sleep is experimentally fragmented. Using PSG, sleep patterns will be experimentally interrupted to the same target level for all subjects during all fragmented nights using auditory procedures to mimic the menopausal hot flash-associated sleep maintenance problem. The in-lab sleep blocks will be conducted: 1) during the mid-to- late follicular phase of the menstrual

cycle when E2 is high; and 2) after at least 4 weeks on leuprolide when HF are prominent in a subset of subjects.

Participants will be given a standardized eucaloric diet for several days preceding the inpatient admission, as well as for the first four days of the inpatient visit. On one day before admission, and on the final day of inpatient admissions, subjects will have an ad lib diet. Fasting adipokine levels will be measured and leptin levels will be obtained to determine the 24-hour leptin profile under standardized eucaloric diet conditions. Food intake and macronutrient composition will be assessed as key behavioral biomarkers for body fat gain when the diet is ad lib. Hunger will be measured under both eucaloric and ad lib dietary conditions. Secondary and exploratory measures of objective HF using skin conductance monitors, negative mood/affect, reward seeking behaviors, and appetite/food preference will also be obtained. Behavioral measures will continue to be assessed at home after the 2nd SB is complete.

Protocol Schema

Study Sample and Criteria

Informed consent will be obtained from up to 130 healthy non-pregnant premenopausal women 18-45 years who do not have hot flashes in order to have 40 women complete study procedures.

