To address **Aim 1** (*impact of menopause-related sleep fragmentation on metabolic and behavioral biomarkers of body fat gain*), the mean levels in each endpoint in response to experimentally fragmented sleep (**Hypothesis 1a & 1b**) will be examined using repeated-measures generalized linear mixed-model regression. Models will incorporate the 2 SB contrasts addressing **Hypothesis 1a and 1b** to simultaneously compare the impact of sleep fragmentation in the HF-free, estrogenized environment (**SB_{SF1} vs. SB_{UD1}**), and hypo-E2 environment with stable HF levels (**SB_{SF2} vs. SB_{UD2}**); exploratory analyses will adjust for HF, either categorized (e.g., any versus none) or number of HF. If there is an omnibus effect of experimental sleep fragmentation, we will conduct post-hoc analyses on each SB contrast to explore whether the impact of experimental sleep fragmentation is consistent across hormonal and HF contexts. To address **Hypothesis 1c**, mean levels in outcomes will be contrasted **SP_{UD3} vs. SP_{UD1}** to assess the impact of sleep disruption related to HF in the environment without experimental sleep fragmentation, comparing those developing HF (expected N=26) with those who do not develop HF; analyses will adjust for initial E2 level.

Aim 2 (*impact of HF on metabolic and behavioral biomarkers of body fat gain*) will be examined using a repeated-measures generalized linear mixed-model regression analysis to determine the effect of HF on mean levels of in metabolic and behavioral biomarkers. The regression will include SB contrasts that assess the impact of HF in the presence (**SB_{SF2} vs. SB_{SF1}**) and absence (**SB_{UD2} vs. SB_{UD1}**) of experimental sleep fragmentation. If an omnibus effect of HF is observed, post-hoc analyses will be conducted on each SB contrast to explore whether the impact of HF is consistent across sleep fragmentation contexts. Additional analyses will substitute objectively measured HF or night-time only HF.

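### Aim 1's check of consistency across hormonal and hot-flash contexts changes both factors at once, and an additive hot-flash adjustment does not separate them

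*SAP*

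**What the plan says.** The Aim 1 paragraph of the SAP builds its model on two within-block contrasts. The first, SF1 vs UD1, is meant "to simultaneously compare the impact of sleep fragmentation in the HF-free, estrogenized environment". The second, SF2 vs UD2, is placed in the "hypo-E2 environment with stable HF levels". Two further steps follow:

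- On hot flashes: "exploratory analyses will adjust for HF, either categorized (e.g., any versus none) or number of HF".
- If the omnibus fragmentation effect is present, each block contrast is examined post hoc to "explore whether the impact of experimental sleep fragmentation is consistent across hormonal and HF contexts".

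The Protocol (Research Design and Methods, Overview) says leuprolide is given "to induce hypo-E2 in all women and generate HF in approximately 2/3, thereby mimicking menopause". For Hypothesis 1c the SAP puts a number on this: "comparing those developing HF (expected N=26) with those who do not develop HF". With 40 completers, that leaves about 14 women who are hypo-estrogenic without HF.

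The SAP does not say whether HF is scored per woman, per block or per night. It names no HF-by-fragmentation term for Aim 1. Where it wants effect modification elsewhere (Exploratory Hypothesis 2) it asks for interaction terms outright, but only with total body fat or visceral adiposity.

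**The concern.** The consistency question has two parts: does the fragmentation effect depend on hormone state, and does it depend on HF? Moving from Block 1 to Block 2 changes both. Every woman goes from estrogenized to hypo-estrogenic, and about 26 of 40 go from no HF to HF. One difference between blocks cannot answer two questions.

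Adjusting for HF looks like the remedy. But the fragmentation contrast lies within a block. If a woman's HF value is the same on her undisturbed and fragmented Block 2 records, an additive HF term cancels from that contrast. An estimate that stays put after adjustment could then be taken as evidence that HF does not matter, although the model never let HF alter the fragmentation effect. At stake is the interpretation of any Block 1 versus Block 2 difference.

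**Working it through.** **Inputs.** 40 completers (SAP, Sample size); 26 expected with HF, hence 40 - 26 = 14 without (SAP, Hypothesis 1c); HF zero in Block 1 (SAP, Aim 1); two-sided alpha 0.05 and 80% power (the SAP gives the levels; two-sidedness is assumed). All simulated effect sizes are assumptions, used only to show the algebra.

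**The plan's own power figures.** They concern correlations, not this contrast, but they reproduce. From r = tanh[(1.960 + 0.842)/sqrt(n - 3)], n = 40 gives 0.431 (stated 0.43 in size) and n = 26 gives 0.526 (stated 0.52; power at 0.52 is 78.9%).

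**Why the additive term cancels.** Write the outcome for woman i, block b, sleep condition s (0 = UD, 1 = SF) as

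y = u_i + block_b + f_b·s + g·H_ib + error,

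with H_i1 = 0 and H_i2 the same for s = 0 and 1. Then SF2 - UD2 = f_2 + error, and g·H_i2 drops out. The block difference f_2 - f_1 is untouched too.

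**What the block difference contains.** If HF changes the fragmentation effect by m and hormone state changes it by h, the average over 40 women is

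block difference = h + (26/40)·m = h + 0.65m.

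That is one equation with two unknowns. For example, assume a fragmentation effect of -1.0 in Block 1 and in HF-free women in Block 2, and -0.3 in women with HF. Block 2 then averages 0.65 × (-0.3) + 0.35 × (-1.0) = -0.545 against -1.0 in Block 1, although h = 0.

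**Simulated check** (40 women, 26 with HF, random woman intercept; the SF column is from models without a block interaction, the SF-by-block column from models with one):

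| Case | HF term | SF estimate (SE) | SF-by-block |
|---|---|---|---|
| HF fixed in Block 2, complete | none | -0.67542 (0.0905) | -0.32178 |
| | any/none | -0.67542 (0.0816) | -0.32178 |
| | number | -0.67542 (0.0787) | -0.32178 |
| HF fixed, 10% of cells missing | none; any/none; number | -0.662; -0.660; -0.649 | -0.261; -0.320; -0.323 |
| Count differs by night type | none | -0.718 | -0.328 |
| | any/none | -0.718 | -0.328 |
| | number | -0.634 | -0.164 |

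In the first case, adding an HF-by-fragmentation term split -0.322 into -0.151 (hormone) and -0.262 (HF). Check: -0.151 + 0.65 × (-0.262) = -0.321, which agrees to rounding. In the last case fragmentation itself was made to raise the count, so adjusting for the count conditioned on a consequence of the exposure.

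**Why a single HF-by-fragmentation term is not enough.** HF is zero for everyone in Block 1, so the block-by-sleep coefficient in that model compares HF-free women in Block 2 with all 40 women in Block 1. In a simulation with no hormone or HF effect, but with HF-prone women already differing in Block 1, it gave -0.22, whereas the paired value within HF-free women was +0.04. The HF-by-sleep term gave a spurious +0.26.

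**Precision.**
- HF vs HF-free difference in SF2 - UD2: (1.960 + 0.842) × sqrt(1/26 + 1/14) = 0.93 SD (normal), 0.95 SD (noncentral t). Power is 31% at 0.5 SD and 65% at 0.8 SD.
- Paired Block 2 minus Block 1 in 14 HF-free women: 0.81 SD (noncentral t), in SDs of a difference of differences. If the two block differences are independent with equal SD, that is 0.81 × sqrt(2) = 1.15 on the first scale.
- HF vs HF-free difference net of Block 1, under the same assumption: 0.953 × sqrt(2) = 1.35.
- For comparison, one paired contrast in all 40 women: 0.45 SD.

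**The case against.** Several points on the other side stand.

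- A reader might infer that the HF adjustment can never change the fragmentation estimate. The documents do not support that. They give no scoring rule and allow a number of HF. HF diaries are completed during the stays and skin conductance may be recorded (Protocol, Detailed Description of Sleep Blocks). For Aim 2 the SAP says "Additional analyses will substitute objectively measured HF or night-time only HF". A night-specific count, or missing cells, does move the estimate.
- The SAP says only that it adjusts; that the term is additive is an inference. It is a fair one, since interactions are named explicitly where they are wanted.
- The SAP gives covariates the purpose of reducing unexplained variability, and in the simulation the HF term did so (SE 0.0905 to 0.0816 or 0.0787). The adjustment is not useless and need not be dropped.
- HF-by-fragmentation is symmetric, and Aim 2 asks whether the HF effect is consistent across sleep contexts. But its named contrasts (SF2 vs SF1, UD2 vs UD1) also cross hormone state. Hypothesis 1c compares women with and without HF only on undisturbed sleep. Neither fills the gap.
- Nothing in the SAP says a Block 2 difference would be credited to hormones, or an unmoved estimate cited as ruling out HF. That risk of interpretation is conjecture.

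**Conclusion.** The point holds in a limited form. The planned consistency check changes hormone state and HF together, and no analysis listed for Aim 1 separates them. An additive HF term leaves the fragmentation contrast and the block difference exactly unchanged when HF is fixed per woman in Block 2 and data are complete. When the count varies by night, the term shifts the estimate only through differences in count between night types, possibly caused by fragmentation. In neither case does it test whether HF modifies the effect.

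It would be wrong to conclude that the trial cannot separate the two factors. The limitation lies in the stated analysis: the 14 or so hypo-estrogenic women without HF give a handle. Separation would still be imperfect, because HF status is not randomised and Block 1 always precedes Block 2.

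The analysis is exploratory and the Aim 1 omnibus test is unaffected, so the weight is minor to moderate. The conclusion assumes the additive reading and the expected 26/14 split. The simulated effects are illustrative and say nothing about the likely size in this trial.

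**What to change.** 1. Define HF once per woman for Block 2: any/none, with number as a second coding.
2. Keep the additive adjustment if wanted for precision, and supplement it with a model containing HF group (develops HF or not), block, sleep condition and all their interactions. This allows for Block 1 differences between women who later do and do not develop HF.
3. Report the fragmentation effect with 95% CI by block and HF group.
4. Judge hormonal-context consistency as the paired Block 2 minus Block 1 difference in the HF-free women.
5. Judge HF-context consistency as the HF vs HF-free difference in SF2 - UD2, shown also net of the same groups' difference in SF1 - UD1.
6. State that these are estimates with CIs and not decisive tests.

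The cost is SAP wording and a few model terms, with no new data. The downside is the low precision shown in the working, which netting out Block 1 may worsen.

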Assessments will be divided into 2 sleep blocks, each of which lasts 9 nights/10 days and includes 5 nights of inpatient laboratory assessment. Each block includes 2 in-lab nights during which sleep is undisturbed and 3 nights during which sleep is experimentally fragmented. Subjects will also receive an actigraphy watch and record their sleep habits before entering the lab, and for up to 7 nights after. During one night of each sleep block, subjects will use an at-home PSG to record their sleep. Subjects will return to BWH the following morning to deposit the PSG device with study staff, and to eat an ad lib breakfast.

- **At-home procedures during the Sleep Block:** Subjects will complete four days of at-home procedures before their admission to the CCI inpatient unit. On the 1st, 2nd, and 4th days, subjects will eat eucaloric meals provided by the BWH Nutrition Core. On the 3rd day, subjects will be given food provided by the Nutrition Core for that entire day, and will be allowed to consume as much as desired at home while logging their meals, snacks and drinks. On the 2nd night of the sleep block, subjects will come to Brigham and Women's to have an at-home ambulatory PSG machine attached; this machine will be removed the following morning when subjects arrive for breakfast. Eucaloric diets will approximate the current American women's diet, with approximately 15% protein, 50% carbohydrates, and 30% fat. Subjects will select each eucaloric meal from options prepared by the Nutrition Core; this selection will be done in advance of sleep blocks. If a subject would like to change their meal preferences, they will be permitted to do so as long as the change can be accommodated by the BWH Nutrition Core. They will be asked to finish meals and log any deviations of the eucaloric diet. For each day with an ad lib diet, caloric intake and macronutrient composition will be calculated and analyzed with Nutrition Data System for Research software after each meal and snack. Subjects will order these meals from a prepared ad lib menu.

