- **Procedures to occur in both SB_{UD} and SB_{SF}:** Subjects will remain indoors during each admission. Technicians will hook subjects up to a PSG monitor each night. Participants will be given a standardized eucaloric diet for the first 5 days of their visit, and will have an ad lib menu on the 6th day of their in-lab stay. On the 6th day, subjects will be given food provided by the Nutrition Core for that entire day, and will be allowed to consume as much as desired at home while logging their meals, snacks and drinks with the app MealLogger™. Subjects will be expected to finish these meals. Caloric and macronutrient intake will be quantified. Fasting adipokine levels, other

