To address **Aim 3** (*impact of estradiol withdrawal on metabolic and behavioral biomarkers of body fat gain*), the mean levels in each endpoint in response to estradiol withdrawal (**Hypothesis 3**) will be examined using repeated-measures generalized linear mixed-model regression. Models will incorporate the 2 estrogenized and hypo-E2 contrasts addressing simultaneously the impact of estradiol withdrawal in the unfragmented and fragmented sleep states. If there is an omnibus effect of estradiol withdrawal, we will conduct post-hoc analyses on each sleep state contrast to explore whether the impact of estradiol withdrawal is consistent across both sleep states. Exploratory analysis will include adjusting for HF – either categorical (yes/no or

none/infrequent/frequent) or continuous – and sleep HF-related disruption in the hypo-E2 state (second SB).

Exploratory Hypothesis #1 analyses will involve a repeated-measures generalized linear mixed-model regression similar to those proposed for the **Hypothesis 1a** analysis using the RQ as an indirect measure of resting EE as the dependent measure, and the same post-hoc paired contrasts and interaction terms for randomization order. **Exploratory Hypothesis #2** analyses will involve addition of interaction terms (between total body fat or visceral adiposity with sleep fragmentation, HF, or E2 withdrawal) to models described for **Aims 1–3**, to test for effect modification on each metabolic or behavioral endpoint. These analyses are by necessity exploratory in nature given the sample size of this complex experimental study. **Exploratory Hypothesis #3** will involve an omnibus repeated-measures regression model encompassing all 6 contrasts described in **Aims 1–3** with the PANAS Negative Affect scale score as the primary predictor and adjustment for fragmented versus undisturbed sleep given an expected association between sleep fragmentation and affect. Post-hoc analyses using paired t-tests on each SB contrast will be conducted to explore the potential variability of the impact of negative affect on each metabolic and behavioral biomarker across the sleep fragmentation, HF, and hormonal contexts. Psychological and cognitive factors driving eating behaviors on the DEBQ will also be explored.

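### Do an odd label in the Hypothesis 1c contrast and a stray order term leave the analyses undefined?

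*SAP*

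**What the plan says.** The Protocol (Research Design and Methods, Overview) sets up two sleep blocks, one before leuprolide and one after it: "Each SB includes 2 nights during which sleep is undisturbed and 3 nights during which sleep is experimentally fragmented". The Detailed Description of Sleep Blocks agrees: "Assessments will be divided into 2 sleep blocks, each of which lasts 9 nights/10 days and includes 5 nights of inpatient laboratory assessment". Crossing block with sleep state gives four conditions: undisturbed (UD1, UD2) and fragmented (SF1, SF2). The Overview describes "open-label treatment with standard-dose depot leuprolide to induce hypo-E2 in all women", so the order of the blocks is the same for everyone.

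The SAP labels its contrasts under Aims 1 and 2 with the prefix SB and an index of 1 or 2. Aim 2, for example, writes the undisturbed comparison across blocks as "SB_{UD2} vs. SB_{UD1". Hypothesis 1c is the exception, with "SP_{UD3} vs. SP_{UD1". Its sentence concerns mean outcome levels without experimental fragmentation. It compares women who develop hot flashes (26 expected) with those who do not, adjusting for initial estradiol.

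Exploratory Hypothesis #1 uses a model like that of Hypothesis 1a, with the same paired contrasts and "interaction terms for randomization order". The Aim 1 text has no such term, and randomization is mentioned nowhere else in either document.

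The readable text does not give the order of nights within a block. The Overview points to a schema, which is a figure that is not shown. It does place the free-choice eating days: "On one day before admission, and on the final day of inpatient admissions, subjects will have an ad lib diet". The Detailed Description likewise says that women "will have an ad lib menu on the 6th day of their in-lab stay".

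**The concern.** Hypothesis 1c is a named hypothesis with its own detectable correlation in the sample-size section, yet its contrast uses a prefix and an index that are defined nowhere. If UD3 counted individual undisturbed nights across blocks, it would be the first such night after leuprolide. The analysis could then use one night or the mean of two, and that choice might be made with the data in hand.

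The order term raises a wider question. Drug and block order are fixed, so only the order of undisturbed and fragmented nights or stays could be randomized. If that order is the same for all women, the term cannot be estimated. More seriously, the fragmentation contrasts behind Hypotheses 1a and 1b would then be mixed with time spent in the lab. The placing of the free-choice eating days suggests that the fragmented nights come last, since only then would the final day follow fragmentation.

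**Working it through.** **Sample-size figures.** Inputs from the SAP, Sample size: n = 40 and 26, α = 0.05 (taken as two-sided), 80% power. With Fisher's z, r = tanh((1.960 + 0.842)/√(n − 3)).

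- n = 40: tanh(2.802/√37) = 0.431, against 0.43 in the SAP.
- n = 26: tanh(2.802/√23) = 0.526, against 0.52 in the SAP.

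Both reproduce closely, and neither uses a contrast label or an order term.

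**The 1c label.** Two blocks × two sleep states = 4 conditions. Aims 1 and 2 give five labelled contrasts: SF1–UD1, SF2–UD2, UD3–UD1, SF2–SF1 and UD2–UD1. Four use only the four conditions. UD3 can be read in three ways:

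| Reading | UD3 means | Contrast |
|---|---|---|
| Slip for UD2 | undisturbed sleep, block 2 | after vs before leuprolide |
| Four sleep periods numbered in turn (UD, SF, UD, SF) | third period, block 2 | the same |
| Undisturbed nights counted 1 to 4 | first undisturbed night, block 2 | the same pair of conditions, one night each |

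All three stay inside the design and compare the same two conditions. The third fits least well. It would make UD2 a night before leuprolide, while Aim 2 uses that index for the condition after it, and no other labelled contrast is at night level. Hypothesis 1c needs hot flashes, which women must never have had at entry, so the later condition must be in block 2. It also excludes experimental fragmentation, so both conditions must be undisturbed. That leaves UD2 against UD1, split by hot-flash status (26 against 40 − 26 = 14).

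What remains open is one night against a two-night mean. Suppose the endpoint is measured after both undisturbed nights, and let ρ be the correlation between them once each woman's own level is removed. The standard-error ratio is then √(2/(1 + ρ)): 1.15 at ρ = 0.5, 1.08 at 0.7 and 1.03 at 0.9. The documents give neither ρ nor nightly measurement, so this range is conditional.

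**The order term.** Take a model with intercept, block, SF, block × SF, order and order × SF, which is 6 columns. With one order for all women, the order column is constant and order × SF is either zero or a copy of SF. The rank is 4, and dropping the two redundant columns leaves the fit and the fragmentation contrasts unchanged. With two orders the rank is 6 and the term can be fitted. This holds with one row per condition as well as one per night.

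**Day in the lab.** Assume nightly data and two undisturbed nights before three fragmented ones for every woman. Day = 1 to 5 and SF = (0, 0, 1, 1, 1) give covariance 0.6, variances 2 and 0.24, and r = 0.6/√0.48 = 0.87. The variance inflation is 1/(1 − 0.75) = 4.0. With day as a category, SF is the sum of the indicators for days 3 to 5, so the two cannot be separated (rank 7 of 8). With each order in half the women, r = 0 and the inflation is 1.0. No SAP model contains a day term, so these figures describe a possible design limit and not the planned analysis.

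**Number of stays.** The Study Procedures Overview lists two stays of five nights under each block, which would be 20 nights; the Overview gives 10. The payment schedule settles it: 100 + 55 + 250 + 10 × 275 + 2 × 700 + 3,500 = 8,055 dollars, the stated maximum. Twenty nights would give 10,805.

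**The case for a change.** The strongest case for a change is that a SAP should fix its contrasts in defined terms, above all for a named hypothesis, and that correcting the wording costs nothing. The night order also matters beyond the exploratory model, because it decides whether the main fragmentation contrasts can be told apart from time in the lab. The documents are not tidy on this. The extra stays in the Study Procedures Overview, and the mention under Foreseeable Risks of fragmentation during only some admissions, read like separate undisturbed and fragmented stays. A randomized order would make sense there.

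Part of this stands. The label is irregular, the order term has no counterpart in the Hypothesis 1a model, and the count of stays is inconsistent. If the order is the same for everyone, a report should say that the fragmented-minus-undisturbed difference also reflects day in the lab.

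What does not stand is the step to a changed analysis. The purpose stated for 1c settles its conditions. The silence on night order can be shown only for the readable text, since the schema is missing and is where such an order would normally appear. If the order is fixed, no rewording of the model would separate fragmentation from lab day.

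**Conclusion.** No change to the plan follows. The 1c label is a clerical slip or an unexplained numbering; analysts would resolve it as undisturbed sleep after against before leuprolide, compared between women with and without hot flashes. The only freedom left is one night against a two-night mean. The mean is what the sentence's reference to mean levels and the condition-level labels elsewhere suggest. The order term sits in one exploratory analysis and either fits or drops out; with a single order, no other estimate moves. The stay count is settled at 10 nights by the Overview and the payment arithmetic. No power figure changes, and no primary result is shown to change.

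This rests on the readable text and on the stated purpose of 1c. The lab-day inflation of 4.0 and the standard-error ratio of 1.03 to 1.15 depend on a night order, nightly measurements and a correlation that the documents do not give, so they do not measure a fault in the plan. Aligning the label and accounting for the order phrase would be good housekeeping, but would not alter what the trial does or can conclude.
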